8.2.1.2 Consumption of N8-GP

Consumption of N8-GP (U/kg BW) during Surgery, Day 0 and Post-operative Period, Days 1-6 and 7-14 must be recorded, see Section [8.5.1](#).

8.2.1.3 Blood Product Transfusions

The following must be recorded for blood product transfusions during Day of Surgery, Visit 2 and hospitalised days in the Post-operative Period:

- Type (e.g red blood cells (RBC) or platelets)
- Haemoglobin (g/dL) prior to RBC transfusion and platelet count ($\times 10^9/L$) prior to platelets transfusion
- Quantity (number of units and mL)
- Start date and time

RBC, platelets and other transfusion products can be administered as clinically warranted. See Section [11](#) for medications not allowed during this trial.

8.2.1.4 Evaluation of Wound Haematoma

To be evaluated upon completion of the surgical procedure at Day of Surgery (Visit 2). Furthermore to be evaluated daily during the Post-operative Period Days 1-6 (Visit 3), once during Days 7-14 (Visit 4) and at EOT Visit.

- Wound haematoma, if assessable: yes /no
 - Estimate volume of wound haematoma (mL), cross sectional area on skin (cm^2)
 - Has the wound haematoma been evacuated: yes/no
 - Text description of wound haematoma evacuation procedure

8.2.1.5 Drain Volume

Drainage to be evaluated daily (within the last 24 hrs \pm 4 hrs) during Day of Surgery, Visit 2 and hospitalised days in the Post-operative Period:

- Yes /no
 - Estimate Volume of drainage (mL)

8.2.1.6 Haemoglobin

At Day of Surgery, Visit 2, haemoglobin must be measured just prior to, during and following surgery, see definition in section [4.3](#) (at 0, 1 hr \pm 20 min and 24 hrs \pm 4 hrs post start of surgery). Exact date and time of sampling must be documented. “Knife to skin” corresponds to time point = 0.

In addition haemoglobin will be assessed by the local laboratory prior to prescribed RBC blood product transfusion.

8.2.2 Bleeding Episodes

During the entire trial period all treatment requiring bleeding episodes will be entered by the patient or caregiver in the patient's eDiary. When the patient is hospitalised or otherwise unable to enter a bleeding episode, the Investigator will have to report in the eCRF, please refer to Section [8.1.6](#). It is always the responsibility of the Investigator to assess the severity of the bleeding episodes and to ensure that all data is recorded correctly in the patient's eDiary.

A treatment requiring bleeding episode is in this trial defined as a bleed that require treatment with a coagulation factor product e.g. N8-GP. If a patient experiences a treatment requiring bleeding episode at home, treatment with N8-GP should be initiated as soon as it is identified and the patient must contact the Investigator immediately and irrespectively of severity of the bleeding episode, please refer to Section [8.2.2](#). When the patient is in contact with the Investigator, it is the responsibility of the Investigator to assess the severity of the bleeding episode. Patients with severe bleeding episodes must visit the site within 24 hrs. For definition of the severity of a bleeding episode please refer to Section [8.2.2.1](#).

Joint bleeds are either categorised as target joint or non-target joint bleeds. Target joints are defined as 3 or more bleeds in the same joint within 6 months. When there has been no bleed in this same joint for 12 months, such a joint is no longer considered a target joint.

From Visit 1 to Visit 2 (Day of Surgery)

All treatment requiring bleeding episodes and any haemostatic treatment administered at home must be recorded in the eDiary.

Day of Surgery

All bleeding episodes and any haemostatic treatment administered must be recorded in the eCRF.

During the Post-operative Period (Days 1-14)

All bleeding episodes occurring during the Post-operative Period (Days 1-14) must be recorded in the eCRF by the investigator/medically qualified person, while the patient is hospitalised. When the patient is discharged from the hospital all bleeding episodes and any haemostatic treatment administered must be recorded in the eDiary by the patient, see Section [8.4.7](#).

If the late Post-operative Period is extended beyond Day 14

The Investigator/medically qualified person must maintain the visit schedule with the patient every week. It is important that the Investigator/medically qualified person reminds the patient or the patient's caregiver to record details on bleeding episodes, their treatment and assessment thereof in the eDiary, see Section [8.4.7](#).

For bleeding episodes the following will be recorded in patient's eDiary or in the eCRF:

- Onset of each bleeding episode (date and time)
- Cause of bleed (spontaneous, traumatic, surgery (minor/major))
- Location of the bleed
- Haemostatic drug used for treatment, dose(s) and time(s) of administration
- Pain relieving medication
- Other therapy used (compression, ice or other)
- Categorisation of bleed (mild/moderate or severe), in the eCRF
- Clinical evaluation of the haemostasis effect (excellent, good, moderate or none)
- Stop of bleed (date and time)

A need for haemostatic rescue therapy with another FVIII product will be assessed by the Investigator via phone or during the site visit. Patients treated with FVIII products other than N8-GP must be withdrawn from the trial.

8.2.2.1 Definition of Severity of Bleeding Episodes:

- **Mild/Moderate:** Bleeding episodes that are uncomplicated joint bleeds, muscular bleeds without compartment syndrome, mucosal- or subcutaneous bleeds
- **Severe:** All intracranial, retroperitoneal, iliopsoas and neck bleeds must be categorised as severe. Muscle bleeds with compartment syndrome and bleeds associated with a significant decrease in the haemoglobin level (>3g/dl) should also be reported as severe. These bleeding episodes must be treated immediately or at the local emergency room and the trial personnel must be contacted. The details of severe bleeding episodes must be entered in the eDiary or if the patient is hospitalised or unable to fill in the eDiary, the Investigator or trial personnel can enter the data in the eCRF. Traumatic bleeds at other locations than described above can always be considered severe at the investigators discretion.

8.2.2.2 Definition of Haemostatic Response

- **Excellent:** abrupt pain relief and/or unequivocal improvement in objective signs of bleeding within approximately 8 hrs after a single infusion
- **Good:** definite pain relief and/or improvement in signs of bleeding within approximately 8 hrs after one infusion, but possibly requiring more than one infusion for complete resolution
- **Moderate:** probable or slight beneficial effect within approximately 8 hrs after the first infusion; usually requiring more than one infusion
- **None:** no improvement, or worsening of symptoms

The assessment for haemostatic response will be made by the patient or patient's caregiver and discussed with the Investigator during visits to the site.

8.2.2.3 Classification of a Bleeding Episode

- spontaneous, traumatic, surgery (minor/major) or re-bleed

A re-bleed is defined as when after an initial period of improvement, there is a worsening of the bleeding site conditions in the same location, either on treatment or *within* 72 hr after stopping treatment. It is considered as a new bleed if worsened >72 hrs after stopping of treatment. Classification of re-bleeds will be done by the trial statistician based on collected trial data at the time of statistical analysis.

8.3 Assessments for Safety

Clinical assessments should preferably be performed prior to blood sampling and trial product administration (where applicable). All assessments/measurements will be recorded in the eCRF unless stated otherwise.

8.3.1 Adverse Events

Monitoring of AEs will be performed from screening to EOT visit, according to the procedures described in Section [12](#).

For recording of bleeding episodes please refer to Section [12.1.3](#).

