4.2.2.3 Health Economics Endpoints

Length of stay in the hospital and days in intensive care will be assessed at the end of the trial.

4.3 Time Frame of the Objectives and Endpoints:

- During surgery is defined as the time from “knife to skin” until “last stitch”
- Day of Surgery is defined as Day 0
- The Post-operative Period is defined as the time from Day 1 to Day 14 (this period can be extended as judged by the Investigator)
- The last visit is defined as the EOT Visit. The EOT Visit cannot be performed sooner than Day 14

5 Trial Design

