6.5 Withdrawal Criteria

The patient may withdraw at will at any time.

The patient may be withdrawn from the trial at the discretion of the Investigator due to a safety concern or if judged non-compliant with trial procedures.

A patient must be withdrawn if the following applies:

1. Haemostasis not achievable with N8-GP: The bleeding episode cannot be controlled after 48 hrs using adequate doses of N8-GP
2. FVIII inhibitor (≥ 0.6 BU/mL) as confirmed by re-testing by central laboratory
3. Allergy/anaphylaxis to the trial product, see Section [8.3.6.3](#) and [12.1.2](#)
4. Usage of Coagulation Factors: FVIII, FIX and FVII-containing products other than N8-GP and other FVIII-containing products like FFP or cryoprecipitate. Bypassing products: rFVIIa, pd-PCC and pd-aPCC
5. Significant thromboembolic event prior to Day of Surgery (Visit 2)
6. Incapacity or unwillingness to follow the trial procedures

7. The planned major surgical procedure is cancelled or postponed

Patients withdrawn from this trial due to cancelled or postponed planned major surgery or unwillingness to perform the surgical procedure are not excluded from continuing in pathfinder™ 2 unless pathfinder™ 2 withdrawal criteria are met.

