Screening failures in pathfinder™ 3 are not excluded from continuing in pathfinder™ 2 unless pathfinder™ 2 withdrawal criteria are met.

For Withdrawn Patients:

Withdrawn patients are defined as patients who meet the withdrawal criteria after dosing, see Section [6.5](#). In case a patient is prematurely withdrawn from the trial the Investigator must aim at undertaking procedures for the EOT Visit as soon as possible, if possible. The primary reason (AE, non-compliance with protocol or other) for discontinuation must be specified in the eCRF. The EOT form must be completed, and final drug accountability must be performed even if the patient is not able to attend. All data collected in the period the patient participated in the trial will be entered into the eCRF. A withdrawal session must be performed in IV/WRS. If a patient is withdrawn due to inhibitor development, the patient must be followed according to section [8.3.6](#).

EOT Visit:

If a patient is withdrawn prior to completion of the trial, all attempts must be made to schedule an EOT Visit for the patient. The EOT form should be signed at the EOT Visit. If a patient continues in FU the EOT form will be signed at the FU Visit.

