8.1.5 Follow-up Visit (only for patients withdrawn due to development of FVIII inhibitors)

In case of withdrawal due to FVIII inhibitor development, the patient should be scheduled for an EOT Visit as soon as possible and within 1 week after a positive inhibitor test is confirmed via re-testing, preferably prior to initiation of treatment with another FVIII product. One month (4 weeks \pm 2 weeks) after the EOT Visit the patient should attend a FU Visit, please see Section [8.3.6](#). At each FU Visit, it will be evaluated if further FU Visits are required. The additional FU Visits will be arranged at intervals of 4 weeks \pm 2 week as long as clinically warranted up until 3 months after confirmation of the FVIII inhibitor.

A wash-out period of minimum 72 hrs is necessary prior to FVIII inhibitors sampling at FU Visit.

The following will be performed and/or recorded in the eCRF:

- Bleeding episodes since last visit
- Vital signs, see Section [8.3.4](#)

Blood sampling for central laboratory assessments:

- FVIII inhibitors, see Section [8.3.6.1](#)

Reminder

- Follow up on any AEs according to Section [12.1](#)
- End of trial
- Affirmation statement

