12.1 Definitions

Adverse Event (AE):

Any untoward medical occurrence in a subject or clinical investigation subject administered a pharmaceutical product, and which does not necessarily have a causal relationship with this treatment.

An AE can therefore be any unfavourable and unintended sign (including an abnormal laboratory finding), symptom, or disease temporally associated with the use of a medicinal product, whether or not considered related to the medicinal product.

Note: This includes events from the first trial related activity after the subject has signed the informed consent and until post treatment follow-up period as defined in the protocol.

An AE can also be a clinical laboratory abnormality regarded as clinically significant i.e. an abnormality that suggests a disease and/or organ toxicity, and is of a severity that requires active management (i.e. change of dose, discontinuation of trial product, more frequent follow-up or diagnostic investigation).

A worsening in concomitant illness must be recorded as an AE. A worsening of an ongoing AE should be reported on a new AE form by making a new assessment for seriousness and/or severity.

The following should **not** be recorded as **AEs**:

- Pre-planned procedures unless the condition for which the procedure was planned has worsened from the first trial related activity after the subject has signed the informed consent
- Pre-existing conditions found as a result of screening procedures. These should be recorded as medical history/concomitant illness.

Serious Adverse Event (SAE):

A SAE is an experience that at any dose results in any of the following:

- Death
- A life-threatening experience ^{a)}
- In-subject hospitalisation or prolongation of existing hospitalisation ^{b)}
- A persistent or significant disability/incapacity ^{c)}
- A congenital anomaly/birth defect
- Important medical events ^{d)} that may not result in death, be life-threatening ^{a)} or require hospitalisation may be considered a SAE when, based upon appropriate medical judgement, they may jeopardise the subject and may require medical or surgical intervention to prevent one of the outcomes listed in this definition.

a) The term “*life-threatening*” - in the definition of SAE - refers to an event in which the subject was at risk of death at the time of the event. It does not refer to an event which hypothetically might have caused death if it were more severe.

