12.2 Collection, Recording and Reporting of Adverse Events

All events meeting the definition of an AE must be collected and reported.

During each contact with the trial site (visit or telephone, excluding the follow up visits due to inhibitor development or safety visits where the subject is not seeing the Investigator or his staff e.g. visit to the laboratory) the subject must be asked about AEs, e.g. "Have you experienced any problems since the last contact?"

All AEs, either observed by the Investigator or reported by the subject, must be recorded by the Investigator and evaluated.

Novo Nordisk' assessment of expectedness is done according to the reference documents:

- Investigator's Brochure, 40K PEG-N8.⁷

The Investigator should record the diagnosis, if available. If no diagnosis is available then the Investigator should record each sign and symptom as individual AEs.

All AEs must be recorded by the Investigator on the standard AE form. If more than one sign or symptom is to be reported use a separate AE form for each sign and symptom. For SAEs complete a safety information form for each event. However, if several symptoms or diagnosis occur as part of the same clinical picture only one set of safety information form pages can be used to describe all the SAEs.

MESIs must always be reported to the department responsible for global product safety on the AE form and the safety information form, irrespective of seriousness within the same timelines as for SAEs.

The Investigator must report initial information on all SAEs and MESIs to Novo Nordisk within **24 hours** of obtaining knowledge about the event.

The Investigator must complete and forward electronically in pdf format/fax copies to Novo Nordisk:

- AE form in the eCRF **within 24 hours**
- safety information form on the paper CRFs **within 5 calendar days** of obtaining knowledge about the SAE.

If for some reason the EDC application is unavailable then the AE information should be reported to Novo Nordisk by fax, telephone or e-mail within the same timelines.

Novo Nordisk must inform the regulatory authorities and IECs/IRBs in accordance with the local requirements in force and ICH GCP.¹⁰

Novo Nordisk will notify the Investigator of trial product related suspected unexpected serious adverse reactions (SUSARs) in accordance with the local requirements. In addition, the Investigator will be informed of any trial related procedure SAEs that may warrant a change of any trial procedure.

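### Adverse event collection can end before Day 14 for operated patients withdrawn for failed haemostasis, allergy or another factor product, because the rules on EOT timing and AE follow-up conflict

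*Combined protocol and SAP*

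**What the plan says.** **End of AE collection.** Section 8.3.1 states: "Monitoring of AEs will be performed from screening to EOT visit". The AE definition in Section 12.1 runs further, "until post treatment follow-up period as defined in the protocol", but the only post-treatment follow-up defined is the FU Visit, which Table 2-1 (footnote 4) reserves for patients with inhibitors. Section 8.1.6 allows Unscheduled Visits only until EOT.

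**Timing of EOT.** Section 4.3 says "The EOT Visit cannot be performed sooner than Day 14"; Table 2-1 (footnote 3) and Sections 8.1, 8.1.3 and 8.1.4 repeat this. For patients withdrawn early, Section 8.1 says "the Investigator must aim at undertaking procedures for the EOT Visit as soon as possible, if possible". Section 6.4 has EOT rescheduled if the patient is bleeding or has had less than 96 hrs of wash-out. None of these provisions says whether it overrides the others after withdrawal.

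**Who is withdrawn.** Section 6.5 makes withdrawal mandatory for failed haemostasis ("The bleeding episode cannot be controlled after 48 hrs using adequate doses of N8-GP"), for allergy or anaphylaxis to the product, and for use of other factor or bypassing products. Amendment 5 narrows the inhibitor criterion to a confirmed titre above 5 BU/mL, or a lower confirmed titre that makes treatment clinically ineffective.

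**Inhibitor follow-up.** Section 8.1.5 plans a FU Visit 4 ± 2 weeks after EOT, with more visits possible up to 3 months. It includes the reminder "Follow up on any AEs according to Section" 12.1, and Table 2-1 marks adverse events in the FU column. Section 12.2 requires patients to be asked about AEs at each contact, "excluding the follow up visits due to inhibitor development".

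**The concern.** The length of safety observation depends on the outcome. A patient whose surgery goes well is watched for at least 14 days. A patient whose bleeding cannot be controlled, who reacts to the product, or who needs another product may be discharged from AE collection within days, while still in the early post-operative period. Any new complication after that point has no planned contact at which it would be picked up.

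AEs and SAEs are a secondary endpoint (Section 4.2.2.2), summarised in Section 18.2.4.1 by frequency of events and of patients with any event, with no mention of observation time. If the patients with the worst course contribute the shortest windows, those frequencies can look more favourable than they should. In a single-arm trial of this size, one or two such patients matter.

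**Working it through.** **1. The plan's own figure.** Section 5.1 gives a trial duration of 2-5 weeks per patient. Screening is 0-3 weeks before surgery and the minimum post-operative period is 14 days: 0 + 14/7 = 2 weeks and 3 + 14/7 = 5 weeks. The stated range is reproduced, so Day 14 is the planned minimum AE window after surgery.

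**2. Earliest withdrawal days.** Allergy or use of another product can occur on Day 0. Failed haemostasis needs 48 hrs, so a bleed starting on Day 0 gives Day 2 at the earliest. Day 6 is added as a later example.

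**3. Days without planned AE collection, out of 14.** Days lost = 14 − EOT day. The wash-out column adds 96 hrs = 4 days and assumes that the last N8-GP dose was on the withdrawal day.

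| Withdrawal | EOT same day | EOT after 96 hrs | Day 14 floor applied |
|---|---|---|---|
| Day 0 | 14 (100%) | 10 (71%) | 0 |
| Day 2 | 12 (86%) | 8 (57%) | 0 |
| Day 6 | 8 (57%) | 4 (29%) | 0 |

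For failed haemostasis on Day 2, the wash-out column is the fairer reading, because Section 6.4 has no written exemption for withdrawals. EOT would be later still if bleeding continued. The first column applies only if sites take Section 6.4 not to cover withdrawn patients.

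**4. Inhibitor withdrawals.** Suppose the confirmatory sample follows a 96 hrs wash-out from Day 0 and laboratory time is zero, so EOT is on Day 4. The FU Visit then falls on Day 4 + 14 = 18 to Day 4 + 42 = 46, nominally Day 4 + 28 = 32. Even with EOT on Day 0, it falls on Day 14 to 42. This group therefore has a planned contact at or beyond the completers' minimum.

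**5. Weight of one patient.** The Safety Analysis Set is all exposed patients, planned at about 18 (Section 6.1), so one patient is 1/18 = 5.6%. The 15 planned surgeries are a less suitable denominator, because Section 6.6 does not count patients withdrawn before completing Day 2 as a surgery. The plan gives no rate of withdrawal by reason.

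**The case against.** The strongest reply is that the Day 14 floor has no exemption for withdrawn patients. Read literally, it removes the shortfall, as the last column of the table shows. That stands as one reading. It cannot be called settled, because Section 8.1 gives the opposite instruction specifically for withdrawals, and Section 8.1.4 wants EOT within 1 week of a confirmed inhibitor, which can fall before Day 14. The text thus contemplates early EOT, and sites could act on either rule.

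Second, serious events are better protected than Section 8.3.1 alone suggests. Section 12.6.3 requires any event after N8-GP that meets SAE or MESI criteria to be reported within 24 hours and states no EOT cut-off. Thromboembolic and allergic events are MESIs (Section 12.1.2), and Section 12.2.1 follows known SAEs and MESIs to outcome. A reader might infer that the Safety Committee would not receive late events; the documents do not support that. What remains is that reporting depends on the investigator learning of an event, and no contact is planned to make that likely.

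Third, a reader might infer that inhibitor withdrawals share the shortened follow-up. They do not: they are the one group with visits planned after EOT. Their problem is the disagreement between Section 12.2 and both Table 2-1 and Section 8.1.5. Even there, Section 12.2 limits only the routine question, still requires AEs observed or reported to be recorded, and its wording can be read as covering only visits where site staff are not seen.

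Fourth, re-bleeding is a weak example of a lost AE. Section 12.1.3 keeps disease-related bleeds out of AE reporting unless they are judged product-related or are fatal.

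Finally, events after withdrawal might be captured in pathfinder 2. Section 6.5 mentions continuing there only after cancelled, postponed or refused surgery, and the pathfinder 2 protocol is not available here, so this cannot be relied on or ruled out.

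**Conclusion.** The point holds for operated patients withdrawn for failed haemostasis, allergy/anaphylaxis or use of another factor or bypassing product. If the prompt-EOT instruction governs, their AE window can close before Day 14 because of a bad outcome, and no later visit is planned. For the Day 2 example the unobserved share is 57% when the wash-out rule is applied and 86% when it is not; it is zero if the Day 14 floor governs. The size therefore rests on which of three unreconciled rules a site follows, and on a withdrawal frequency that the documents do not give.

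The loss is mainly active collection of new AEs, with less certain detection of new SAEs and MESIs. It does not extend to SAEs and MESIs already known. For inhibitor withdrawals, the defect is conflicting instructions on AE questioning at the FU Visit. This should be corrected: the gap is outcome-dependent and cheap to close.

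**What to change.** 1. In Sections 8.3.1, 8.1 and 8.1.4, state that AEs, SAEs, MESIs, bleeding episodes, transfusions and haemostatic products used are collected to at least Day 14 for every operated patient, whatever the reason for withdrawal and even if EOT procedures are done earlier. Telephone contact or the hospital record suffices, subject to consent.
2. Reconcile the prompt-EOT instruction in Section 8.1 with the Day 14 floor (Table 2-1, Sections 4.3, 8.1 and 8.1.4) and the rescheduling rule in Section 6.4, so that one rule on EOT timing applies after withdrawal.
3. Delete the exclusion of inhibitor follow-up visits from the AE question in Section 12.2, so that it agrees with Table 2-1 and Section 8.1.5.
4. Report post-operative AE observation time per surgery beside the AE tables.

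The cost is protocol wording and one telephone contact or chart check per withdrawn patient. Some added events will have occurred under other products, so the product in use at onset should be shown. No treatment or withdrawal rule changes.
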